10.6. Appendix 6: Kidney Safety: Monitoring Guidelines

10.6.1. Laboratory Assessment of Change in Kidney Function and Detection of Kidney Injury

Standard kidney safety monitoring requires assessment of baseline and postbaseline Screat measurement to estimate kidney function [Screat-based eGFR] or creatinine clearance [eCrCl]). Obtaining Screening or Baseline Scys and postbaseline reflex Scys (if confirmed Screat increase ≥0.3 mg/dL) makes it feasible to distinguish AKI from DICI. If Screat increase is confirmed after baseline, then reflex measurement of Scys is indicated:

ADULTS: Currently, 2021 CKD-EPI eGFR equations (Screat only-based and combined Screat plus Scys-based) are valid for use in adults only. At baseline Screat and Scys values are needed to calculate 2021 CKD-EPI eGFR by Screat only-based equation (see Table 10.6.2.1) and by combined Screat plus Scys-based equation. When post-baseline Screat increase ≥0.3 mg/dL is confirmed, then reflex Scys measurement is needed to enable post-baseline comparison of eGFR changes (Screat only-based eGFR and combined Screat plus Scys eGFR).

Regardless of whether kidney function monitoring tests are required as a routine safety monitoring procedure in the study, if the investigator or sponsor deems it necessary to further assess kidney safety and quantify kidney function, then these test results should be managed and followed per standard of care.

10.6.2. Age-Specific Kidney Function Calculation Recommendations

10.6.2.1. Adults (18 Years and Above)—2021 CKD-EPI Equations

eGFR (mL/min/1.73m²)⁸

2021 CKD- EPI	Screat (mg/dL)	Seys (mg/L)	Recommended eGFR Equation
Screat Only			
Female	if ≤ 0.7	NA	$eGFR = 143 \times (Screat/0.7)^{-0.241} \times (0.9938)^{Ago}$
Female	if > 0.7	NA	$eGFR = 143 \times (Screat/0.7)^{-1.200} \times (0.9938)^{Ago}$
Male	if ≤ 0.9	NA	eGFR = 142 × (Screat/0.9) ^{-0.302} × (0.9938) ^{Ago}
Male	if > 0.9	NA	$eGFR = 142 \times (Screat/0.9)^{-1.200} \times (0.9938)^{Ago}$
2021 CKD-	Screat	Scys	Recommended eGFR Equation
EPI	(mg/dL)	(mg/L)	_
Screat-Scys			
Combined			
Female	if ≤ 0.7	if ≤ 0.8	$eGFR = 130 \times (Screat/0.7)^{-0.219} \times (Scys/0.8)^{-0.323} \times (0.9961)^{Age}$
Female	if ≤ 0.7	if > 0.8	$eGFR = 130 \times (Screat/0.7)^{-0.219} \times (Scys/0.8)^{-0.778} \times (0.9961)^{Ago}$
Female	if > 0.7	if ≤ 0.8	$eGFR = 130 \times (Screat/0.7)^{-0.544} \times (Scys/0.8)^{-0.323} \times (0.9961)^{Ago}$
Female	if > 0.7	if > 0.8	$eGFR = 130 \times (Screat/0.7)^{-0.544} \times (Scys/0.8)^{-0.778} \times (0.9961)^{Ago}$
Male	if ≤ 0.9	if ≤ 0.8	eGFR = 135 × (Screat/0.9) ^{-0.144} × (Scys/0.8) ^{-0.323} × (0.9961) ^{Ago}
Male	if ≤ 0.9	if > 0.8	eGFR = $135 \times (Screat/0.9)^{-0.144} \times (Scys/0.8)^{-0.778} \times (0.9961)^{Age}$
Male	if > 0.9	if ≤ 0.8	$eGFR = 135 \times (Screat/0.9)^{-0.544} \times (Scys/0.8)^{-0.323} \times (0.9961)^{Ago}$
Male	if > 0.9	if > 0.8	eGFR = 135 × (Screat/0.9)-0.544 × (Scys/0.8)-0.778 × (0.9961)Ago

10.6.3. Adverse Event Grading for Kidney Safety Laboratory Abnormalities

AE grading for decline in kidney function (ie, eGFR or eCrCl) will be according to Kidney Disease: Improving Global Outcomes (KDIGO) criteria for adult participants.

KDIGO criteria grade (G)	Study Population	Gl	G2	G3	G4	G5
Decreased Kidney Function due to either Acute or Chronic Kidney Injury	Adult participants eGFR (mL/min/1.73m²)	≥90	≥60 to 89	30 to 59	15 to 29	<15

KDIGO albuminuria (A) criteria	Al	A2	A3
Albumin-to-creatinine ratio (ACR)	<30 mg/g	30 to 300 mg/g	>300 mg/g
	OR	OR	OR
	<3 mg/mmol	3 to 30 mg/mmol	>30 mg/mmol

10.7. Appendix 7: ECG Findings of Potential Clinical Concern

ECG Findings That May Qualify as AEs

- Marked sinus bradycardia (rate <40 bpm) lasting minutes.
- New PR interval prolongation >280 ms.
- New prolongation of QTcF to >480 ms (absolute).
- New prolongation of QTcF by >60 ms from baseline.
- New-onset atrial flutter or fibrillation, with controlled ventricular response rate: ie, rate <120 bpm.
- New-onset type I second-degree (Wenckebach) AV block of >30-second duration.
- Frequent PVCs, triplets, or short intervals (<30 seconds) of consecutive ventricular complexes.

ECG Findings That May Qualify as SAEs

- QTcF prolongation >500 ms.
- Absolute value of QTcF > 450 ms AND QTcF change from baseline >60 ms.
- New ST-T changes suggestive of myocardial ischemia.
- New-onset LBBB (QRS complex>120 ms).
- New-onset right bundle branch block (QRS complex>120 ms).
- Symptomatic bradycardia.
- Asystole
 - In awake, symptom-free participants in sinus rhythm, with documented asystolic pauses ≥3 seconds or any escape rate <40 bpm, or with an escape rhythm that is below the AV node;
 - In awake, symptom-free participants with atrial fibrillation and bradycardia with 1 or more asystolic pauses of at least 5 seconds or longer.
- Atrial flutter or fibrillation, with rapid ventricular response rate: rapid = rate
 >120 bpm.

- Sustained supraventricular tachycardia (rate >120 bpm) ("sustained" = short duration with relevant symptoms or lasting >1 minute).
- Ventricular rhythms >30 seconds' duration, including idioventricular rhythm (HR <40 bpm), accelerated idioventricular rhythm (HR >40 bpm to <100 bpm), and monomorphic/polymorphic ventricular tachycardia (HR >100 bpm [such as torsades de pointes]).
- Type II second-degree (Mobitz II) AV block.
- Complete (third-degree) heart block.

ECG Findings That Qualify as SAEs

- Change in pattern suggestive of new myocardial infarction.
- Sustained ventricular tachyarrhythmias (>30-seconds duration).
- Second- or third-degree AV block requiring pacemaker placement.
- Asystolic pauses requiring pacemaker placement.
- Atrial flutter or fibrillation with rapid ventricular response requiring cardioversion.
- Ventricular fibrillation/flutter.
- At the discretion of the investigator, any arrhythmia classified as an adverse experience.

The major events of potential clinical concern listed above are recommended as "alerts" or notifications from the core ECG laboratory to the investigator and Pfizer study team, and not to be considered as all-inclusive of what is to be reported as AEs/SAEs.

10.8. Appendix 8: Drug Product Acceptability Questionnaire Protocol ID: C5091013 Visit: DATE OF VISIT DD MMM YYYY

DRUG PRODUCT ACCEPTABILITY QUESTIONNAIRE

☐ (1) NOT DONE Language administered: ☐ English

Drug Product Acceptability Questionnaire

INSTRUCTIONS TO SITE: This questionnaire should be distributed to and filled out by participants immediately after having taken the study product on Day 1, each period.

Please ask the participant to view the tablets in the cup without touching them before ingesting the study product and before completing the questionnaire.

Please collect the questionnaire when complete. Please confirm that the questionnaire is complete. If there are missing items, please return the questionnaire to the participant and ask them to complete the missing items.

Please record the following information:

Study#/Study Site	
Period and Day	
Collect Date	
Collect Time	
Participant ID (Rand ID)	
Collected by	
Entered in PIMS by	
Checked in PIMS by	
Questionnaire Fully Completed (circle)	Yes/No

		CENTER			P	PARTICIPANT ID							
	Protocol ID: C5091013												
Visit: _		DA	TE O	7	Т	-			-		П		
		VIS	SIT	L	┸	IJ L			J L				
					DD		MN	ſΜ		Y	YYY		
DRUG P	PRODUCT ACCEPTABILITY	QUESTION	NAIR	Е									
□ (1) N(OT DONE. Language adn	ninistered	XI F	nglish									

Drug-Product Acceptability Questionnaire

Please tell us how much you agree or disagree with each of the following 14 statements by circling the number corresponding to your answer:

		Strongly Agree	Agree	Neither Agree nor Disagree	Disagree	Strongly Disagree
1.	The surface of the tablets looked rough (not smooth)	1	2	3	4	5
2.	The tablets had an odd shape (not round, oval, or capsule-shaped)	1	2	3	4	5
3.	The color of the tablets was not attractive	1	2	3	4	5
4.	The tablets felt chalky or rough in my mouth	1	2	3	4	5
5.	The tablets stuck to the inside of my mouth	1	2	3	4	5
6.	The tablets felt waxy in my mouth	1	2	3	4	5
7.	The tablets began to dissolve in my mouth before I swallowed them	1	2	3	4	5
8.	The tablets tasted bitter	1	2	3	4	5
9.	The tablets had a smell	1	2	3	4	5
10.	When I took the tablets, I had a burning sensation in my mouth or on my tongue	1	2	3	4	5
11.	When I took the tablets, I had a burning sensation in my throat	1	2	3	4	5
12.	The tablets were too big to swallow	1	2	3	4	5
13.	The tablets were difficult to swallow	1	2	3	4	5
14.	Overall, these tablets were difficult to take	1	2	3	4	5

10.9. Appendix 9: Abbreviations

The following is a list of abbreviations that may be used in the protocol.

Abbreviation	Term
Abs	absolute
ACR	albumin-to-creatinine ratio
ADL	activity/activities of daily living
AE	adverse event
AESI	adverse event of special interest
AKI	acute kidney injury
ALT	alanine aminotransferase
ARDS	acute respiratory distress syndrome
AST	aspartate aminotransferase
AUC ₂₄	area under the plasma concentration-time profile from time 0 to the time 24 hours
AUCinf	area under the plasma concentration-time profile from time 0 extrapolated to infinity
AUClast	area under the plasma concentration-time profile from time 0 to the time of the last quantifiable concentration (C _{last})
AV	atrioventricular
AxMP	auxiliary medicinal product
β-hCG	β-human chorionic gonadotropin
BID	twice daily
BMI	body mass index
BP	blood pressure
bpm	beats per minute
BSA	body surface area
BUN	blood urea nitrogen
C ₁₂	concentration at 12h nominal time post-dose
CFR	Code of Federal Regulations
CI	confidence interval
CIOMS	Council for International Organizations of Medical Sciences
CK	creatine kinase
CKD-EPI	chronic kidney disease epidemiology
CL	total clearance of drug
CL/F	apparent clearance
C _{last}	last quantifiable concentration
C_{max}	maximum observed concentration
CO ₂	carbon dioxide (bicarbonate)
COVID-19	coronavirus disease 2019
CRF	case report form
CRO	contract research organization
CRU	clinical research unit
CSR	Clinical Study Report

Abbreviation	Term
CT	clinical trial
CTIS	Clinical Trial Information System
CTMS	Clinical Trial Management System
CYP	cytochrome P450
CV	cardiovascular
DCT	data collection tool
DDI	drug-drug interaction
DICI	drug-induced creatinine increase
DIKI	drug-induced kidney injury
DILI	drug-induced liver injury
DMID	dosage material identification
EC	ethics committee
ECC	emergency contact card
ECG	electrocardiogram or electrocardiography
eCrCl	estimated creatinine clearance
eCRF	electronic case report form
EDB	exposure during breastfeeding
E-DMC	External Data Monitoring Committee
EDP	exposure during pregnancy
eGFR	estimated glomerular filtration rate
EMA	European Medicines Agency
eSAE	electronic serious adverse event
ET	early termination
EU	European Union
EudraCT	European Union Drug Regulating Authorities Clinical Trials
	(European Clinical Trials Database)
FDA	US Food and Drug Administration
$\mathbf{f_m}$	fraction metabolized
FSH	follicle-stimulating hormone
$\mathbf{f}_{\mathbf{u}}$	fraction unbound
F/U	follow-up
G1 to G5	KDIGO eGFR category standardization
GCP	Good Clinical Practice
GD	gestation day
GFR	glomerular filtration rate
GGT	gamma-glutamyl transferase
GLP	Good Laboratory Practice
HBcAb	hepatitis B core antibody
HBsAb	hepatitis B surface antibody
HBsAg	hepatitis B surface antigen
HCoV-229E	human coronavirus 229E
HCVAb	hepatitis C antibody
HIV	human immunodeficiency virus

Abbreviation	Term
HR/hr	heart rate/hour (based on the content)
HRT	hormone replacement therapy
B	Investigator's Brochure
IC ₅₀	inhibitory concentration 50%
ICD	informed consent document
ICH	International Council for Harmonization of Technical Requirements
	for Pharmaceuticals for Human Use
ID	identification
IMP	investigational medicinal product
IND	Investigational New Drug
INR	international normalized ratio
IP	investigational product
IPAL	Investigational Product Accountability Log
IRB	Institutional Review Board
IV	intravenous(ly)
K	Proportionality constant for Schwartz Equations (kidney function)
KDIGO	Kidney Disease Improving Global Outcomes
k _{el}	first-order elimination rate constant
Ki	inhibition constant
LBBB	left bundle branch block
LFT	liver function test
MAD	multiple ascending dose
MCH	mean corpuscular hemoglobin
MCHC	mean corpuscular hemoglobin concentration
MCV	mean corpuscular volume
CCI	
ME	Metabolism and Excretion
MERS-CoV	middle east respiratory syndrome coronavirus
M ^{Pro}	main protease
MQI	medically qualified individual
MTD	maximum tolerated dose
NA	not applicable
NHP	non-human primates
NIMP	non-investigational medicinal product
NOAEL	no observed adverse effect level
ICCI	
PE	physical examination
PI	principal investigator
PIMS	Phase 1 Management System
PK	pharmacokinetic(s)
1 1 1 1 1	pharmacokinetic(s)

Abbreviation	Term
PSSA	Pfizer's Serious Adverse Event Submission Assistant
PT	prothrombin time
PVC	premature ventricular contraction/complex
QRS	A combination of three of the graphical deflections seen on a typical
_	electrocardiogram
QTc	corrected QT interval
QTcF	QTc corrected using Fridericia's formula
qual	qualitative
rBA	relative bioavailability
RBC	red blood cell
RNA	ribonucleic acid
RR	resting rate
RRCK	Ralph Russ canine kidney cells RRCK
SAE	serious adverse event
SAD	single ascending dose
SAP	Statistical Analysis Plan
SARS-CoV-2	severe acute respiratory syndrome coronavirus 2
SARS-CoV-2 Mpro	the main protease of SARS-CoV-2
Scr	serum creatinine
Screat	serum creatinine
Scys	serum cystatin C
SD	single dose
SDD	spray dried dispersion
SoA	schedule of activities
SOP	standard operating procedure
SRSD	Single Reference Safety Document
ST-T	ST-segment and T-wave
SUSAR	Suspected Unexpected Serious Adverse Reaction
t½	terminal half-life
T bili	total bilirubin
TEAE	treatment emergent adverse event
THC	tetrahydrocannabinol
T _{max}	time for C _{max}
ULN	upper limit of normal
US	United States
UTI	urinary tract infection
UV-Vis	ultraviolet-visible spectroscopy
V _{ss}	steady-state volume of distribution (=CL MRT)
V _z /F	apparent volume of distribution
WBC	white blood cell
WHO	World Health Organization
WOCBP	woman/women of childbearing potential

1. VERSION HISTORY

Table 1. Summary of Changes

Version/ Date	Associated Protocol Amendment	Rationale	Specific Changes
1	Original	N/A	N/A
22 Nov 2023	24 Aug 2023		

2. INTRODUCTION

This statistical analysis plan (SAP) provides the detailed methodology for summary and statistical analyses of the data collected in Study C5091013.

This document may modify the plans outlined in the protocol; however, any major modifications of the primary endpoint definition or its analysis will also be reflected in a protocol amendment.

Text in *italics* is taken directly from the protocol.

2.1. Modifications to the Analysis Plan Described in the Protocol

No modifications.

2.2. Study Objectives, Endpoints, and Estimands

Туре	Objective	Endpoint	Estimand			
Primary:	Primary:					
PK (Section 3.1)	To determine the oral bioavailability of test oral formulations of PF-07817883 relative to the reference oral formulation.	Cmax and AUCinf if data permit, otherwise AUClast.	N/A			
Seconda	ry:					
Safety (Section 3.1)	To evaluate the safety and tolerability of PF-07817883 formulations in healthy participants.	Assessment of TEAEs, clinical laboratory abnormalities, vital signs, and 12-lead ECGs.	N/A			
Tertiary/	Exploratory:					
PK (Section 3.4.1)	To characterize the PK of PF-07817883 after single oral dose of PF-07817883 formulations.	Plasma PK parameters: Tmax, C ₁₂ , and if data permit Vz/F, CL/F and t½.	N/A			
Other (Section 3.4.2)	To assess the drug product acceptability of PF-07817883 formulations.	Assessment of drug product acceptability via a questionnaire.	N/A			

2.3. Study Design

This is a Phase 1, open-label, randomized, 4-period, 4-sequence crossover study in healthy adult participants evaluating the rBA of 3 new PF-07817883 test oral formulation(s) compared to PF-07817883 reference oral formulation. Approximately 12 participants will be enrolled in this study with approximately equal number of participants randomized to 1 of 4 sequences (Table 2). The new formulations used for each treatment as defined in Table 2 will be decided based on the availability of new formulations.

A sample size of approximately 12 participants with 8 completers was chosen to provide adequate precision to compare the relative bioavailability of test formulations of PF-07817883 relative to the reference formulation in Periods 1 through 4.

A sample study design schematic is presented in Figure 1.

[figure not shown]
Table 2. Study Design

Sequence	Period 1	Period 2	Period 3	Period 4
1 (n=3)	Α	В	С	D
2 (n=3)	В	D	Α	С
3 (n=3)	С	Α	D	В
4 (n=3)	D	С	В	Α

Treatment A = PF-07817883 300 mg reference formulation, fasted, DP-006067, 23-DP-01449

Treatment B = PF-07817883 300 mg test formulation 1, fasted, DP-006067, 23-DP-01526 Treatment C = PF-07817883 300 mg test formulation 2, fasted, DP-006973, 23-DP-01687 Treatment D = PF-07817883 300 mg test formulation 3, fasted, DP-006974, 23-DP-01696

Figure 1. Schema

DMID. lot numbers:

A: DP-006067, 23-DP-01449 B: DP-006067, 23-DP-01526 C: DP-006973, 23-DP-01687 D: DP-006974, 23-DP-01696

3. ENDPOINTS AND BASELINE VARIABLES: DEFINITIONS AND CONVENTIONS

3.1. Primary Endpoint(s)

Blood samples for PK analysis of PF-07817883 will be taken according to the SoA in the protocol.

Plasma PK parameters of PF-07817883 will be derived (as data permit) from the concentration-time data using standard noncompartmental methods as outlined in Table 3 Actual PK sampling times will be used in the derivation of PK parameters. In the case that actual PK sampling times are not available, nominal PK sampling time will be used in the derivation of PK parameters.

concentration (C_{last}).

Maximum observed

concentration

Method of **Parameter Definition Analysis Scale Analysis Determination** Method AUC_{inf}* Area under the A, D $AUC_{last} + (C_{last}*/k_{el}),$ ln concentration-time where C_{last}* is the curve from time 0 predicted plasma extrapolated to concentration at the infinity last quantifiable time point from the loglinear regression analysis AUC_{last}a A, D Area under the Linear/Log ln trapezoidal method. plasma concentration-time profile from time 0 to the time of the last auantifiable

Table 3. Summary of PF-07817883 plasma PK parameters to be calculated.

 C_{max}

from data

Observed directly

ln

A, D

Abbreviations: A=analyzed using a statistical model (if applicable); D=displayed with descriptive statistics as outlined in Table 5 in Section 6.1; In=natural-log transformed;.

3.2. Secondary Endpoint(s)

Secondary endpoints include assessment of adverse events (AEs), clinical safety laboratory abnormalities, vital signs and ECG parameters.

The following data are considered in standard safety summaries (see protocol for collection days and list of parameters):

- adverse events,
- laboratory data (except data from screening visit),
- · vital signs data,
- ECG results

3.2.1. Adverse Events

An adverse event is considered a Treatment-Emergent Adverse Event (TEAE) if the event started during the effective duration of treatment. All events that start on or after the first dose of study intervention, but before the end of the study will be flagged as TEAEs. The algorithm will not consider any events that started prior to the first dose date.

Events that occur in a non-treatment period (e.g., washout or follow-up) will be counted as treatment emergent and attributed to the most recent treatment taken.

^{*}If data permit.

a. 48h PK sample in Periods 1 to 3 will be considered 0h PK sample for the subsequent period.

A 3-tier approach for summarizing adverse events (AEs) will not be used due to the low number of participants planned to be recruited.

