4. STUDY DESIGN

4.1. Overall Design

This is a Phase 1, open-label, randomized, 4-period, 4-sequence crossover study in healthy adult participants evaluating the rBA of 3 new PF-07817883 test oral formulation(s) compared to PF-07817883 reference oral formulation. Approximately 12 participants will be enrolled in this study with approximately equal number of participants randomized to 1 of 4 sequences (Table 2). The new formulations used for each treatment as defined in Table 2 will be decided based on the availability of new formulations.

Table 2. Study Design

Sequence	Period 1	Period 2	Period 3	Period 4
1 (n=3)	A	В	C	D
2 (n=3)	В	D	A	C
3 (n=3)	C	A	D	В
4 (n=3)	D	С	В	A

Treatment A = PF-07817883 300 mg reference formulation, fasted, DP-006067, 23-DP-01449

Treatment B = PF-07817883 300 mg test formulation 1, fasted, DP-006067, 23-DP-01526

Treatment C = PF-07817883 300 mg test formulation 2, fasted, DP-006973, 23-DP-01687

Treatment D = PF-07817883 300 mg test formulation 3, fasted, DP-006974, 23-DP-01696

Healthy participants will be screened to determine eligibility within 28 days prior to study treatment. Participants will report to the CRU on Period 1 Day -1 (Study Day -1) and will be required to stay at the CRU until discharge. The participants will remain confined at the CRU until all assessments in all periods are complete.

In each period on Day 1, following an overnight fast of ~10h, participants will receive one of the treatments as defined in Table 2. Serial plasma PK samples will be collected up to 48 hours following the dose, at times outlined in the SoA. Participants will also complete a drug-product acceptability questionnaire shortly after receiving PF-07817883 in each period. At least 48 hours of washout between the doses of PF-07817883 administered to a participant in consecutive periods will be implemented. Dosing in the subsequent periods can take place immediately following the last PK sample collection of a period (SoA, Section 5.3).

A follow-up (which may be a phone call) will be made to participants approximately 28 to 35 days from administration of the final dose of study intervention.

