4.2. Scientific Rationale for Study Design

This study will evaluate bioavailability of 3 new tablet formulations (test) of PF-07817883 relative to the current formulation (reference) in healthy participants.

Based on the median half-life of hr, observed in C5091008 study, which also used 300 mg immediate release tablet formulation as a SD; the hr washout interval is deemed sufficient to provide the concentration <5% of C_{max} in the subsequent period.

In study C5091001, administration of PF-07817883 oral suspension with high-fat meal decreased AUC_{last} and C_{max} by and %, respectively. Thus, to avoid the potential effect of food on PF-07817883 PK, the participants will be dosed in fasted state in all periods.

Drug product acceptability questionnaire is an exploratory endpoint to inform the future product development.

Based in the formulation, the test and reference formulations are expected to have a very similar safety profile. In order to limit the study-burden to a participant, post-dose safety labs/ECG are not proposed in each period.

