8.4.1. Time Period and Frequency for Collecting AE and SAE Information

The time period for actively eliciting and collecting AEs and SAEs ("active collection period") for each participant begins from the time the participant provides informed consent, which is obtained before undergoing any study-related procedure and/or receiving study intervention), through and including a minimum of 28 calendar days after the last administration of the study intervention.

Follow-up by the investigator continues throughout the active collection period and until the AE or SAE or its sequelae resolve or stabilize at a level acceptable to the investigator.

When a clinically important AE remains ongoing at the end of the active collection period, follow-up by the investigator continues until the AE or SAE or its sequelae resolve or stabilize at a level acceptable to the investigator and Pfizer concurs with that assessment.

For participants who are screen failures, the active collection period ends when screen failure status is determined.

If the participant withdraws from the study and also withdraws consent for the collection of future information, the active collection period ends when consent is withdrawn.

If a participant permanently discontinues or temporarily discontinues study intervention because of an AE or SAE, the AE or SAE must be recorded on the CRF and the SAE reported using the CT SAE Report Form.

Investigators are not obligated to actively seek information on AEs or SAEs after the participant has concluded study participation. However, if the investigator learns of any SAE, including a death, at any time after a participant has concluded study participation, and they consider the event to be reasonably related to the study intervention, the investigator must promptly report the SAE to Pfizer using the CT SAE Report Form.

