6.2.1. Adverse Events

AEs will be listed and summarized by treatment and overall and in accordance with sponsor reporting standards using the safety population defined in Section 4.

Incidence and severity of TEAE tables will additionally be produced ('All causality' and 'Treatment related,' separately) to summarize the total number of adverse events by preferred term, which will be reported by treatment and overall, in accordance with sponsor reporting standards using the safety analysis set defined in Section 4.

The AEs will be presented sorted in descending frequency based on the overall number of AEs (by preferred term or system order class as appropriate) across treatments.

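### About 80% of each formulation's AE at-risk time is late follow-up in the three people who took it last; add a common-window TEAE table

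*SAP*

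**What the plan says.** **Attribution.** SAP 3.2.1 sets one TEAE window for the whole study: "All events that start on or after the first dose of study intervention, but before the end of the study will be flagged as TEAEs". Events in washout or follow-up "will be counted as treatment emergent and attributed to the most recent treatment taken". The section refers to an effective duration of treatment but gives it no length within a period.

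**Tabulation.** Under SAP 6.2.1, "AEs will be listed and summarized by treatment and overall". TEAE incidence and severity tables follow, all-causality and treatment-related separately. No onset cut-off or exposure adjustment is stated, and SAP 6.6.3 marks treatment exposure as not applicable. The section defers to sponsor reporting standards, which are not reproduced.

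**Timing.** Protocol 4.1 states: "At least 48 hours of washout between the doses of PF-07817883 administered to a participant in consecutive periods will be implemented". It adds: "Dosing in the subsequent periods can take place immediately following the last PK sample collection of a period". After the last period, "A follow-up (which may be a phone call) will be made to participants approximately 28 to 35 days from administration of the final dose". Protocol 8.4.1 has active AE collection run "through and including a minimum of 28 calendar days after the last administration of the study intervention".

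**Design.** Table 2 (Protocol 4.1, SAP 2.3) gives sequences ABCD, BDAC, CADB and DCBA, with 3 participants each. Each formulation is last in exactly one sequence: D in 1, C in 2, B in 3, A in 4.

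**The concern.** The secondary objective is the safety and tolerability of the formulations (Protocol 3), and the results are to inform formulation selection (Protocol 2.1). The strength of a crossover is that each participant is observed under every formulation. The attribution rule keeps that for the first 48 h or so after each dose. It then adds a tail of several weeks, which goes wholly to the formulation taken last.

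In that tail each formulation is represented by a different group of three people, all of whom have by then taken all four formulations. Much of the tail also has little to do with the drug. For the washout, Protocol 4.2 says that the "washout interval is deemed sufficient to provide the concentration <5% of C_{max} in the subsequent period". The interval in that sentence is blacked out; Protocol 4.1 gives it as at least 48 h. An unrelated illness in week 3 would count in the all-causality column of whichever formulation the sequence placed last. Each column's incidence also mixes nine people at risk for about 2 days with three at risk for 28 to 35 days.

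**Working it through.** The documents give no figure for AE observation time per formulation, so there is none to reproduce. The allocation figures in Protocol 9.5 agree with each other: 4 × 3 = 12 randomized and 4 × 2 = 8 completers.

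**Inputs.** 12 completers, 3 per sequence (Table 2). Window W = 2 days in Periods 1 to 3 (Protocol 4.1). Window F = 28 or 35 days after Period 4 (Protocol 4.1 and 8.4.1).

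**At-risk time per formulation.** Nine participants take a given formulation in a non-final period and three take it last.

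| Quantity | Formula | F = 28 | F = 35 |
|---|---|---|---|
| Periods 1 to 3 | 9 × 2 | 18 | 18 |
| Period 4 and follow-up | 3 × F | 84 | 105 |
| Total participant-days | sum | 102 | 123 |
| Share from the three who take it last | 3F / total | 84/102 = 82.4% | 105/123 = 85.4% |
| Share beyond 48 h post-dose | 3(F − 2) / total | 78/102 = 76.5% | 99/123 = 80.5% |
| Window ratio, last to earlier | F / 2 | 14 | 17.5 |

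The shares are the same if only the 2 completers per sequence are counted: 56/68 = 82.4% and 70/82 = 85.4%.

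**Longer washout (assumption).** Protocol 4.1 says at least 48 h. With W = 3 days, the share beyond W is 75/111 = 68% to 96/132 = 73%. With W = 4 days, it is 72/120 = 60% to 93/141 = 66%.

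**From time to events.** The first 48 h after all doses gives 12 × 2 = 24 participant-days per formulation; the tail gives 78 to 99. Let r be the AE rate in the first 48 h divided by the later rate. The tail then holds 78/(78 + 24r) to 99/(99 + 24r) of expected events:

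- r = 1: 76% to 80%
- r = 2: 62% to 67%
- r = 3: 52% to 58%
- r = 5: 39% to 45%

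The tail ceases to be the majority at r = 78/24 = 3.25 (F = 28) or 99/24 = 4.1 (F = 35). The documents give no event timing, so r is unknown.

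**Balance.** Each formulation is last once. With full completion all four columns therefore have the same total, 102 to 123 participant-days.

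**Loss of balance.** Protocol 9.5 plans on 8 completers out of 12, which allows about 4 non-completers. Suppose only one of the three in a sequence reaches Period 4, and ignore other effects of dropout. The formulation that is last in that sequence then has 18 + 28 = 46 or 18 + 35 = 53 participant-days, against 102 or 123 for the others.

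**With a common 48 h window.** Each formulation has 12 × 2 = 24 participant-days, of which each sequence supplies 3 × 2 = 6 (25%).

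**The case against.** The case for leaving the plan alone has several parts.

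- **The rule is explicit and balanced.** This stands. It is prespecified and reproducible, and with full completion it favours no formulation. Equal totals do not, however, make the tail a within-participant comparison. Balance also depends on completion, although participants who stop for non-safety reasons may be replaced at the sponsor's discretion.
- **Time is not events.** This stands. A reader might infer that most AEs in each column will be late follow-up events. The documents do not support that: it needs r below about 3.3 to 4.1. AEs are also monitored throughout confinement, whereas follow-up may be a single telephone contact.
- **The crossover comparison survives.** This stands for the first 48 h. A reader might infer that the table becomes a parallel comparison of four groups of three. It does not: every completer contributes about 48 h to every column, and only the tail is between-person.
- **The treatment-related table separates background events.** It does so in part. Causality is judged open-label, and the all-causality table has no such protection.
- **Little rests on the table.** There are no hypotheses or decision rules, the formulations are expected to have very similar safety profiles, and the primary PK analysis is unaffected. This limits the weight of the point.
- **A strict 48 h cut would do harm.** It would fall on the Day 3 laboratory, ECG and vital-sign assessments of the last period, and would move delayed related events out of every formulation column. This is a good reason not to replace the planned tables, but no reason against adding to them.

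A reader might also infer that each early stop adds about 26 days (28 − 2) to one column. The documents do not settle this. Protocol 7.1 says that a participant permanently discontinued from study intervention does not remain for further evaluation. Protocol 7.2.1 keeps those who ask to stop in follow-up, and 8.4.1 collects AEs for at least 28 days after the last dose. These passages need to be reconciled.

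**Conclusion.** The point holds as one about at-risk time and precision, not about bias. Most of each formulation's observation time (76.5% to 80.5%) lies beyond 48 h post-dose in three people of one sequence, given 12 completers, a 2-day window in Periods 1 to 3 and 28 to 35 days of follow-up. A washout of 3 or 4 days would lower that share to between 60% and 73%. No formulation is systematically favoured under full completion. What is lost is clarity: between-person noise is added to a within-participant comparison that the design already provides, and non-completion can make the windows unequal. The endpoint is descriptive and secondary, and the sponsor's reporting standards cannot be seen and might add detail. This is an inexpensive improvement, not an error that threatens the study's conclusions.

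**What to change.** Keep the most-recent-treatment attribution in SAP 3.2.1, the planned tables and the listing. In SAP 6.2.1, add by-formulation TEAE incidence and severity tables, all-causality and treatment-related, limited to a common window in all four periods. The window runs from each dose to the next dose or through completion of the Day 3 (48 h) assessments, whichever is earlier. Ending it at completion of those assessments keeps findings first detected on Day 3 of Period 4 inside the window. Show later-onset events in a separate follow-up row by last treatment and sequence, and in the overall column.

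The cost is one onset flag on data already collected, a short addition to the SAP and an extra set of tables. Delayed reactions would not appear in the common-window columns, but they remain in the follow-up row, the overall column, the planned full-attribution tables and the listing.
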